PGC-1a measurements. Blood samples will be collected in the morning, after an overnight fast and withholding all morning medications. Samples will be obtained at baseline and at the monthly visits throughout the trial. PGC-1a RNA and protein from peripheral blood mononuclear cells (PMBC's) will be measured by qRT-PCR and enzyme-linked immunosorbent assay (ELISA) respectively. RTPCR will be performed by the ABI PRISM 7900HT Sequence Detection System (Applied Biosystems, Foster City, CA). Each 25µl reaction consists of PGC-1a specific primers (Hs01016719_m1), cDNA template and qPCR gene expression Mastermix (Life technologies). Cycle threshold values for each reaction are adjusted automatically, and the fold changes are determined. The fold-changes values are derived relative to control and are represented as means + SEMs of mRNA expression normalized to β -actin and comparison made using ANOVA PGC-1a protein expression will also be performed using a PGC-1a ELISA kit (USA biological) as per the instructions of the manufacturer.

Adverse Events. We will monitor for known side effects of fenofibrate including, but not limited to,

myalgia, elevated blood pressure, and specifically alterations in hepatic or renal function, and photosensitivity using a questionnaire specifically designed for this purpose, blood pressure readings, and blood tests of renal and hepatic function at every monthly visit. In accordance with the recommendation in the package insert for fenofibrate, serum level of HDL-C will be assesses at Baseline Visit, week 12 and week 24. There are no contraindications for concurrent statin and fenofibrate use, but idiopathic myopathy and myositis are more common among patients treated with both agents. Fenofibrate is the only fibrate that does not appear to produce a substantial pharmacokinetic effect on statin elimination. Subjects can withdraw for any reason at any time.

5. List up to ten relevant references/articles to support the rationale for the research. Do not append an extensive NIH-grant-style bibliography.

REFERENCES

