- Baseline Visit creatinine greater than 2.0 mg/dL.
- History of gallstones.
- Use of Coenzyme Q10 at a dose greater than 600 mg daily within 30 days of Baseline Visit.
- Current or history of substance (alcohol or drug) abuse within one year of baseline visit.
- Current or recent (within 3 months of screen visit) use of dopamine blocking agents such as:
 - o tetrabenazine
 - o antipsychotics
 - o metoclopramide
 - o prochlorperazine

• HAART

- and any current or recent (within 3 months of screen visit) fibrate medication (fenofibrate, gemfibrozil, clofibrate, bezafibrate, ciprofibrate, or clinofibrate).
- Diagnosis of myopathy/myositis.
- Current use of Warfarin (Coumadin).
- Current use of statins (e.g., Simvastatin, Atorvastatin, etc.)
- Clinical evidence of unstable medical illness according to judgment of the investigator.
- Clinical evidence of unstable psychiatric illness, including psychosis, untreated major depression, or suicidal ideation within 90 days prior to baseline visit.

2. If eligibility is based on age, gender, pregnancy/childbearing potential, social/ethnic group, or language spoken (e.g., English Speakers only), provide a scientific rationale.

[] Not applicable: Subject eligibility is not based on these factors.

Genetic testing of subjects under the age of 18 is highly discouraged for genetic counseling purposes due to the inability to treat the disease in any way, and to allow individuals to perform informed consent when they reach adulthood. Because of the complex considerations of predictive genetic testing for HD, minors are excluded from this study.

Most of the families seen in the clinic speak English, even if as a second language. The cognitive testing tools employed in this study have not all been validated in languages other than English. Subjects will therefore be required to be proficient in spoken and written English.

SECTION 4: RECRUITMENT METHODS

Check any of the following methods that will be used to recruit subjects for this study:

[] This study involves no direct contact with subjects (i.e., use of existing records, charts, specimens).

Specify database or IRB-approved protocol number (HS#), if applicable: <Type here>

[X] Advertisements, flyers, brochures, email, Facebook, and/or other media.

Specify where recruitment materials will be posted: Gottschalk Medical Plaza, UCI HD Clinic

If subjects will be recruited by mail, e-mail, or phone, specify how their contact information will be obtained: <Type here>

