- For women of childbearing potential, review of acceptable birth control methods that must be used during the study

All potential participants who meet the eligibility criteria after this screening will be scheduled for the Baseline visit within 14 days.

Baseline Visit.

The following baseline visit procedures will be performed within 14 days from the screening visit:

- Conduct final review of eligibility (prior to first dose). Subjects must continue to meet all inclusion and exclusion criteria at the Baseline Visit.
- Obtain vital sign measurements
- Complete all sections of the UHDRS (Motor, Cognitive, Behavioral, Functional, Independence, and TFC).
- Assess predominant HD symptoms (must be completed by the site investigator)
- Complete Neuropsychological Tests (Hopkins Verbal Learning Test-Revised, Symbol Digit Modalities Test, UHDRS Cognitive, Stroop Word and Benton Judgment of Line Orientation)
- Review concomitant drug usage
- Assess adverse events
- Instruct subject about correct administration of study drug
- Provide instructions to subject and caregiver (if applicable) on study drug consumption, compliance, and reporting of adverse experiences

This visit should take about 2-3 hours.

Following phlebotomy subjects will receive calories and fluids (e.g., energy bar and juice) and then undergo clinical evaluations, including UHDRS, cognitive tests, and CGI-S. Upon conclusion of clinical evaluations the study procedures will be reviewed with the subject and the one month supply of study medication will be provided.

Monthly Visits. The 6, monthly visits will involve a fasting blood draw, a brief clinical examination and completion of an adverse events questionnaire. A pill count will be done to monitor study drug compliance. Monthly visits are expected to last 30 minutes to one hour. The 3- and 6-month visits will include administration of the UHDRS, MoCA, Neuropsychological exams and the CGI.

Randomization. The first 20 participants eligible for the trial after screening will be randomly assigned to either the active drug or placebo group at a 3:1 ratio. Enrollment ID Numbers will be developed by the study statistician and will correspond to specific study drug vials. Study drug will be labeled with a four-digit Enrollment ID Number assigned to that subject.

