We will allow patients using statins to enroll in the study because recent guidelines from the American College of Cardiology and the American Heart Association now recommend the use of these drugs in adults as primary preventative therapy for heart disease.

Blinding. The randomization assignment for each participant will be blinded to all clinical investigators and known only to the study statistician who will perform the randomization and maintain the randomization key. Group assignment will be un-blinded after the clinical trial is complete, or if there is a medical emergency for the participant which requires this.

Study Drug. All subjects will receive a one month supply of study medication from the Study Coordinator at the baseline visit and at subsequent monthly visits for a total of 6 months of drug. All study medications (active drug and placebo) will be prepared in identical appearing capsules. The approved dosing of fenofibrate is in 48mg, 96mg, and 145mg capsules with a maximum dose of 145mg per day. Participants assigned to the active drug group will take a single 145mg capsule of fenofibrate daily during the study and participants assigned to the placebo group will take a single, identical appearing inert capsule daily during the study. We will utilize the maximum tolerated dose for each subject beginning at 145mg per day and reduce the dose if significant side effects are encountered (see Adverse Events).

2. Provide precise definitions of the study endpoints and criteria for evaluation; if the primary outcomes are derived from several measurements (i.e., composite variables) or if endpoints are based composite variables, then describe precisely how the composite variables are derived.

Table	2.	Study	Outcomes
-------	----	-------	----------

Outcome	Туре	Measure
Primary Outcome	PGC-1 α activity	Leukocyte PGC-1a RNA and protein concentrations
Secondary	Fenofibrate	Plasma fenofibrate levels
Outcome		
Secondary	Motor	Unified Huntington Disease Rating Scale (UHDRS)
Outcome		Motor
Secondary	Cognition	Montreal Cognitive Assessment (MoCA)
Outcome		
Secondary	Psychiatric	Unified Huntington Disease Rating Scale (UHDRS)
Outcome		Behavioral
Secondary	Functional	Clinical Global Impression (CGI-I)
Outcome		

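### Section 3.C.1 excludes current statin users, but a sentence repeated in Sections 6.B.1 and 6.C.1 lets them enroll, and no available text reconciles the two

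*Combined protocol and SAP*

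**What the plan says.** The exclusion list in Section 3.C.1 of the combined protocol and SAP includes "Current use of statins (e.g., Simvastatin, Atorvastatin, etc". No reason is given.

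Section 6.B.1, directly after its Randomization paragraph, has a sentence that begins "We will allow patients using statins to enroll in the study because recent guidelines from the American College of Cardiology" and goes on to give primary prevention of heart disease as the reason. Section 6.C.1 carries the same sentence inside its own Randomization paragraph.

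Section 6.B.1 also sets out how eligibility is checked. The Screening Visit list includes a review of the criteria and of current and past drug use. The Baseline Visit list adds "Conduct final review of eligibility (prior to first dose" and states "Subjects must continue to meet all inclusion and exclusion criteria at the Baseline Visit". Table 1 in 6.B.1 marks the criteria review at both visits.

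The Adverse Events paragraph in Section 1.4 comments on the drug combination: "There are no contraindications for concurrent statin and fenofibrate use", but "idiopathic myopathy and myositis are more common among patients treated with both agents". It adds: "Fenofibrate is the only fibrate that does not appear to produce a substantial pharmacokinetic effect on statin elimination".

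**The concern.** A patient on a statin is ineligible under one section and may be enrolled under two others. Both statements are current text, and the permission looks deliberate because it comes with a reason. Recruitment includes screening medical records for eligibility (Section 4), so the question can arise before a patient is even approached.

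What is at stake is safety and adherence to the protocol, not the inference. Admitting a statin user breaches a listed exclusion and exposes that patient, if assigned to fenofibrate, to a combination that the protocol itself associates with more muscle disease. Section 7.B lists muscle symptoms among the risks of fenofibrate but does not mention statins or the combination.

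**Working it through.** There is no planned figure to reproduce. The check sets the statements side by side.

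1. **Do the two rules cover the same patients?** Yes. Section 3.C.1 concerns current use, and the sentence in 6.B.1 and 6.C.1 concerns patients using statins at enrolment. Other drug exclusions in 3.C.1 carry qualifiers: fibrates and dopamine blockers have a 3-month window, and Coenzyme Q10 has a dose limit of 600 mg daily and a 30-day window. The statin bullet has none, and the permission has none either. No subgroup, dose or period lets both be true.

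2. **Is one of them superseded?** Nothing shows this. Both stand in the body of the protocol, and there is no amendment log or precedence statement in the available text.

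3. **Does the trial flow in 6.B.1 settle it?** It leans towards the exclusion. The criteria and drug use are reviewed at Screening, and the criteria again at Baseline before the first dose, so a statin user meets the exclusion list twice. The randomization step, "The first 20 participants eligible for the trial after screening will be randomly assigned", also refers back to eligibility. But the very next sentence treats statin users as people who may be eligible, so the flow does not expressly cancel the permission.

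4. **Does the flow in 6.C.1 settle it?** No. Its Screening text collects medication information and names grounds for exclusion: TFC below 7, raised transaminases, creatinine above 2.0 mg/dl, low HDL-C, or another significant blood abnormality. Statins are not named. It refers to the eligibility criteria in general terms, but its Table 1 has no row for criteria review (it does have a medication review at every visit), and its Baseline text has no final check. The one explicit statement on statins in 6.C.1 is that users may enroll.

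5. **Does Section 1.4 settle it?** No. It gives one reason for caution and two reasons for tolerance of the combination, and sets no eligibility rule.

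6. **Size.** The documents give no statin prevalence for the clinic population and no myopathy rate for the combination, so neither the number of patients affected nor the added risk can be computed. The allocation does give one figure. At 3:1 with 20 randomized, 20 × 3/4 = 15 receive fenofibrate and 20 × 1/4 = 5 receive placebo. A statin user who is randomized therefore has a 3-in-4 chance of receiving the combination. The sample-size statement (15 subjects, 80% power, alpha 0.05) makes no use of statin status and is unaffected.

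**The case against.** The strongest reply is that the two rules do not weigh the same. Section 3.C.1 is the only formal list of criteria. Section 6.B.1 applies that list at Screening and again before the first dose. The permissive sentence is a single sentence copied into a second place, so its two appearances are not two independent statements. This stands, and it makes mistaken enrolment less likely. It does not remove the conflict, because 6.C.1 contains the permission without the reviews.

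A reader might infer that following either rule breaches the other. The documents do not support that. The sentence grants a permission; declining a statin user leaves it unused and exposes nobody to the combination. The breach and the risk run one way, towards enrolling a barred patient.

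A reader might also infer that Section 1.4 contradicts the exclusion. It does not: it is background, and its remark about contraindications is followed in the same sentence by the warning about muscle disease.

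The muscle safeguards are real: exclusion of diagnosed myopathy or myositis, a monthly questionnaire that covers myalgia, medication review at every visit, and dose reduction for significant side effects. Apart from the myopathy exclusion they act after enrolment, and none of them decides whether a statin user may enter.

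**Conclusion.** The contradiction is real and should be resolved before enrolment. It lies between one bullet in 3.C.1 and one sentence repeated in 6.B.1 and 6.C.1. The exclusion is the more operative rule under 6.B.1; the permission is the only explicit statin rule in 6.C.1. The consequence is a route by which a barred patient could receive a combination that the protocol links to more myopathy and myositis.

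The conclusion has limits:

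- The number of patients who would be affected is unknown, and nothing here shows that statin users will in fact be enrolled.
- Alpha, power and sample size do not change.
- The lack of a rule for statins started after baseline might be taken as part of the error. It is a separate gap in detail and does not bear on which entry rule applies.
- The silence of 7.B on the combination does not show what participants are told, since the consent pages are not available.
- Pages after the Section 2 heading are also missing from the available copy. The conclusion assumes that they hold no statin rule, which is likely given that the heading concerns the study team.

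**What to change.** Before enrolment, keep the statin exclusion in 3.C.1 and delete the sentence that begins "We will allow patients using statins to enroll in the study because recent guidelines from the American College of Cardiology" from both 6.B.1 and 6.C.1. Leave the 3:1 randomization text intact.

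The cost is one deletion in two places, with no extra patients, visits or tests. Recruitment narrows only if the permission was the intended rule, because 3.C.1 as written already excludes these patients. If it was intended, make the opposite change: delete the statin bullet in 3.C.1 and state the combination's muscle risk in 7.B.

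Three additions are optional and not needed to remove the contradiction: a cross-reference to the chosen rule in Section 1.4, a rule for statins started after baseline, and a listing of muscle adverse events by arm and statin use. With about 5 participants on placebo, such a listing could only be descriptive.

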Category/Group (e.g., adults, controls, parents, children)	Age Range (e.g., 7-12, 13–17, adults)	Maximum Number to be Consented or Reviewed/Collected (include withdrawals and screen failures)	Number Expected to Complete the Study or Needed to Address the Research Question
Adults, with a positive gene test with > 36 CAG repeats within the previous six (6) months	21-85, inclusive	25	20
		- /	

Total: 25

B. Overall Study Sample Size

If this is a multi-site study, provide the total number of subjects to be enrolled from all sites.

[X] Not applicable: This study will only take place at UCI, and does not involve other sites.

Total number of subjects across all sites is 25.

C. Eligibility Criteria

1. Identify the criteria for inclusion and exclusion.

Inclusion criteria:

- Adults of either sex, ages 18 or older.
- Subjects must have clinical findings of Huntington's disease and a confirmatory family history of Huntington's disease, or clinical findings of Huntington's disease and a CAG repeat expansion of > 36.
- Subjects must have a score of \geq 7 on the Total Functional Capacity (TFC) scale.
- Proficiency with written and spoken English and corrected vision or hearing to complete the cognitive testing.
- Subjects must be capable of providing informed consent and complying with study procedures.
- Subjects must be able to take oral medication.
- Good overall health status with no known problems anticipated over the course of the trial.
- Women of child bearing potential (i.e., not postmenopausal or surgically sterile) must have a negative pregnancy test, be non-lactating and use adequate contraception methods during the study. Adequate contraception methods include abstinence, oral, implanted or injected contraceptives (e.g., birth control pills, intrauterine device), barrier (e.g., vaginal ring or diaphragm/cervical cap with spermicide), transdermal patch and/or partner vasectomy. Reliable contraception must be in use 30 days prior to Baseline Visit.

Exclusion criteria:

- History of known sensitivity or intolerance to any fibrate medication.
- Exposure to an investigational medication within the 30 days prior to baseline visit.
- Other major neurological disease [e.g., multiple sclerosis, Parkinson's disease, cortical stroke, etc]
- Clinically significant hepatic disease, gallbladder, or severe renal dysfunction, including primary biliary cirrhosis, and unexplained persistent liver function abnormality.

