Potential participants will be recruited from the UCI HD clinic where the study will be described to potential subjects. If the candidate is interested in participating, informed consent and Health Insurance Portability and Accountability Act of 1996 (HIPPA) authorization will be obtained. After consent, potential participants will be scheduled for the Screening Visit.

			1-	2-	3-	4-	5-	6-
	Screeni	Baselin	mont	mont	mont	mont	mont	mont
	ng Visit	e Visit	h	h	h	h	h	h
			visit	visit	visit	visit	visit	visit
Consenting	Х							
Review								
Inclusion/Exclusi	Х	X						
on Criteria								
Demographics								
and family and	Х							
medical history								
Vital signs	Х	Х	Х	Х	Х	Х	Х	Х
Renal and								
hepatic blood	Х	X	Х	Х	Х	Х	Х	Х
tests								
Concomitant								
medication	Х	X	Х	Х	Х	Х	Х	Х
review								
PGC1- α levels	Х	Х	Х	Х	Х	Х	Х	Х
Fenofibrate		v	v	Y	Y	Y	Y	Y
levels			^	~			~	~
Motor,								
Cognitive,								
Psychiatric,	Х	X			Х			Х
Functional								
measures								

Table 1.Study Schema

Clinical neurological and physical examination	х	х			x			x
Study drug reconciliation and dispensing		х	х	х	х	х	х	х
Adverse events questionnaire			Х	Х	Х	Х	Х	Х

Procedures: The trial will last 6-months and will require eight study visits: A Screening Visit and Baseline Visit prior to drug and a monthly visit for the 6-month trial (**Table 1. Study Schema below**). All visits will include: a fasting blood draw for leukocyte PGC-1α protein and transcript levels, and plasma fenofibrate levels; medication and medical history update; adverse events questionnaire; study drug accounting and distribution. The Baseline 3-month, and final 6-month study visit will include administration of the UHDRS, MoCA, and CGI (**Table 2. Study Outcomes**). Participants will be provided food and drink following the blood draw and before any clinical examinations and cognitive testing.

Screening Visit.

The following procedures will be performed at the Screening Visit (Visit SC):

- Obtain written informed consent (if not already obtained)
- Subject Number assigned
- Inclusion/exclusion criteria review
- Demographics
- Medical history
- Review concomitant and prior drug usage
- Obtain vital sign measurements
- Conduct general physical exam
- Conduct general neurological exam
- UHDRS Total Functional Capacity (TFC)
- Blood specimen collection for safety laboratory tests, including BUN, creatinine, ALT, AST, hematology, and serum pregnancy test for women of childbearing potential.

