Baseline Visit. The baseline visit will be completed within 14 days of the Screening Visit and prior to the administration of any study medication. We will collect a fasting blood sample for baseline leukocyte PGC-1 α protein and transcript levels. We will administer the full UHDRS and neuropsychological tests. In addition, the study procedures will be reviewed and a 1-month supply of study medication will be distributed.

Monthly Visits. The 6, monthly visits will involve a fasting blood draw, and query regarding adverse events by the investigators. A pill count will be done to monitor study drug compliance. Monthly visits are expected to last 30 minutes to one hour. The 3- and 6-month visits will include administration of the UHDRS, MoCA, Neuropsychological exams and the CGI.

Randomization. The first 20 participants eligible for the trial after screening will be randomly assigned to either the active drug or placebo group at a 3:1 ratio. We will allow patients using statins to enroll in the study because recent guidelines from the American College of Cardiology and the American Heart Association now recommend the use of these drugs in adults as primary preventative therapy for heart disease.

Blinding. The randomization assignment for each participant will be blinded to all clinical investigators and known only to the study statistician who will perform the randomization and maintain the randomization key. Group assignment will be un-blinded after the clinical trial is complete, or if there is a medical emergency for the participant which requires this.

2. Describe the duration of a subject's participation in the study. If there are sub-studies, include duration of participation in each sub-study.

Subject's participation will include a Screening and Baseline Visit as well as six (6) monthly follow-up visits. Total time for participant's participation is approximately 10 hours over a 7 month period.

3. List data collection instruments (e.g., measures, questionnaires, interview questions, observational tool, etc.).

Investigator-authored, non-standardized, or un-validated measures must be submitted for review.

-Demographics

- -Medical History
- -Unified Huntington Disease Rating Scale (UHDRS) Motor
- -Unified Huntington Disease Rating Scale (UHDRS) Behavioral
- -Montreal Cognitive Assessment (MoCA)
- -Clinical Global Impression (CGI)
- -Neurological examination
- -Physical examination

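### The only scheduled pregnancy test is at Screening; none is listed at Baseline or during six months on a drug the plan calls a possible fetal hazard

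*Combined protocol and SAP*

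**What the plan says.** Under Section 3.C.1, women of childbearing potential "must have a negative pregnancy test, be non-lactating and use adequate contraception methods during the study". No visit or time window is given for that test. Reliable contraception has to be in place 30 days before Baseline.

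The Section 6.B.1 Screening list includes a "serum pregnancy test for women of childbearing potential" and a "review of acceptable birth control methods that must be used during the study". Baseline follows within 14 days. Its final eligibility review states "Subjects must continue to meet all inclusion and exclusion criteria at the Baseline Visit", but its procedure list contains no pregnancy test.

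For the dosing period, Section 6.B.1 says "The 6, monthly visits will involve a fasting blood draw, a brief clinical examination and completion of an adverse events questionnaire". Section 6.C.1 says "The 6, monthly visits will involve a fasting blood draw, and query regarding adverse events by the investigators". The Procedures text in both sections has all visits include "medication and medical history update; adverse events questionnaire; study drug accounting and distribution". Study drug is given out one month at a time, "at the baseline visit and at subsequent monthly visits for a total of 6 months of drug".

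Section 7.B states the fetal risk and asks subjects to contact the researchers at once if they or a partner become pregnant.

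**The concern.** The plan names a fetal hazard, admits women who could conceive, and supplies drug for six months, yet lists no objective check for pregnancy after Screening. The other safeguards are real. Contraception lowers the chance of conception but does not detect a failure. The medical update, the adverse event questions and the instruction to report a pregnancy work only once the woman knows or suspects that she is pregnant.

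Two groups are exposed. A woman who conceived too shortly before Screening for the test to show can receive her first dose. A woman who conceives later can be handed further monthly supplies until she notices. What is at stake is participant and fetal safety. The primary endpoint, the power and the analysis are not affected.

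**Working it through.** **Where a pregnancy test is listed**

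| Place | Pregnancy test listed? |
|---|---|
| 6.B.1 Screening list | Yes (serum) |
| 6.C.1 Screening text | No (CBC, ALT, AST, BUN, creatinine, HDL-C) |
| Baseline, 6.B.1 and 6.C.1 | No (6.B.1 has a general eligibility re-check) |
| Monthly visits, 6.B.1 and 6.C.1 | No |
| Monthly safety bloods, Section 1.4 | No (renal and hepatic function) |
| Table 1 in 6.B.1 and in 6.C.1 | No row |

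One of 8 visits lists a test. Baseline plus 6 monthly visits gives 7 later blood draws with none listed.

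**Age of the only result.** At first dose it is up to 14 days old. At last dose, with 30-day months, it is 14 + 180 = about 194 days old.

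**Days on study drug after a conception during dosing (illustrative).** The plan gives no figure to reproduce. These are assumptions, not document values:

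- The conception day c is uniform on 0 to 180, and visits fall at days 0, 30, ..., 180.
- The test turns positive L = 14 days after conception.
- The woman notices R = 28, 56 or 84 days after conception.

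*As written*, drug stops at the earlier of c + R and day 180, so mean exposure is R − R²/(2 × 180):

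- R = 28: 28 − 784/360 = 25.8
- R = 56: 56 − 3136/360 = 47.3
- R = 84: 84 − 7056/360 = 64.4

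*With a test before each supply*, drug stops at the first visit on or after c + L, if that is earlier. For conceptions in the first five months the wait W is uniform on 14 to 44 days, so exposure is capped at 14 + 30 = 44. In the sixth month, end of dosing limits exposure to V, uniform on 0 to 30. Mean exposure is [5 × E min(W, R) + E min(V, R)]/6:

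- R = 28: E min(W, 28) = (14 × 21 + 16 × 28)/30 = 24.73, and E min(V, 28) = (28²/2 + 2 × 28)/30 = 14.93. The mean is (5 × 24.73 + 14.93)/6 = 23.1.
- R = 56 or 84 (both above 44): (5 × 29 + 15)/6 = 26.7.

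*With tests at months 3 and 6 only*, the month 3 test acts on conceptions up to day 76. For R = 56 the sum over conception days is 34 × 56 + 42 × 35 + 48 × 56 + 56²/2 = 7630, and 7630/180 = 42.4. The same method gives 25.3 for R = 28 and 50.8 for R = 84.

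| Noticed at (days) | As written | Monthly tests | Saved | Months 3 and 6 | Saved |
|---|---|---|---|---|---|
| 28 | 25.8 | 23.1 | 2.7 | 25.3 | 0.5 |
| 56 | 47.3 | 26.7 | 20.6 | 42.4 | 4.9 |
| 84 | 64.4 | 26.7 | 37.7 | 50.8 | 13.6 |

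With L = 10 the cap is 40 days and monthly tests save 4.5, 24.0 and 41.1 days. These are days on study drug. Under 3:1 randomization, 75% of subjects take fenofibrate, so the expected fenofibrate days saved at L = 14 are 0.75 times the monthly figures: about 2.0, 15.5 and 28.3.

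**The case against.** The lists in this document are plainly incomplete. Neither Table 1 shows the Screening pregnancy test that the 6.B.1 list requires, and the HDL-C tests at weeks 12 and 24 in Section 1.4 appear in neither table. A missing row is therefore weak evidence that no test was intended. This has force for Baseline, where the demand that all criteria still be met could be read as requiring a fresh negative test. It can equally be read as satisfied by the Screening result, so the wording needs settling. It does not help the dosing period, for which no available text mentions a test.

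It is also fair to say that the plan has layered safeguards, that testing frequency on top of mandatory contraception is a judgement, and that the documents cite no rule requiring monthly tests. The exposure figures depend on a conception having occurred and on assumed recognition times. The monthly saving ranges from 2.7 to 37.7 days on that assumption alone. The month 6 test saves no exposure if dosing ends then, so in the months 3 and 6 comparison the whole saving comes from month 3. The benefit of a Baseline test is not in the model. All of this stands and limits how much weight the figures can bear, but it does not supply a test during dosing.

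Finally, the consent pages and the adverse events questionnaire are not shown. A rule that drug stops on pregnancy may be stated there, so its absence here adds no weight.

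**Conclusion.** The concern holds. In the available text one pregnancy test, at Screening, covers six one-month supplies of a drug the plan regards as a possible fetal hazard. Followed as written, the plan would keep dispensing to a woman with an unrecognised pregnancy. The gain from monthly testing is small if pregnancies are noticed early and substantial if they are noticed late. Testing does not prevent conception on drug; it limits undetected exposure afterwards to about one supply plus the test lag. With few women likely to be affected, a serious possible consequence and a very low cost, this is a change the plan should make. Confidence is medium, because of the Baseline ambiguity and the unseen consent pages and questionnaire.

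**What to change.** For women of childbearing potential, add a urine test, or a serum test on blood already drawn, at Baseline before the first dose, before each monthly dispensing, and at month 6. State that a positive result stops study drug and that the pregnancy is followed to outcome. Add a pregnancy-test row to both Table 1s, including the existing Screening test, and list that test in the Section 6.C.1 Screening text. The month 6 test serves mainly to detect a pregnancy for follow-up; both tables also mark dispensing at month 6, which should be reconciled with six months of drug. If the sponsor's reproductive safety information supports a longer interval, state the interval and the reason.

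The cost is up to 7 inexpensive tests per woman of childbearing potential, or at most 7 × 20 = 140 if every randomized subject were one. No extra visit or needle stick is needed. The downside is an occasional false positive, which needs a repeat test and may briefly delay dispensing.
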